5.3.1. Meals and Dietary Restrictions

Patients should continue their usual exercise habits and generally follow a healthy meal plan (with consistent meal size and time of day) throughout the course of the study. Dietary counseling may be reviewed throughout the study, as needed.

In addition, patients should not receive an intensive diet/exercise program with the intent of reducing body weight at any time during the study, other than the lifestyle and dietary measures for diabetes treatment.

5.4. Screen Failures

Screen failures are defined as participants who consent to participate in the clinical study but are not subsequently randomly assigned to study intervention. A minimal set of screen failure information is required to ensure transparent reporting of screen failure participants to meet the Consolidated Standards of Reporting Trials (CONSORT) publishing requirements and to respond to queries from regulatory authorities. Minimal information includes demography, screen failure details, eligibility criteria, and any SAE.

Individuals who do not meet the criteria for participation in this study (screen failure) may be rescreened once. The interval between screening and rescreening should be at least 4 weeks. A new ICF must be signed at the time of rescreening and the study participant will be assigned a new identification number. A single repeat testing of suspected erroneous/spurious central laboratory results is allowed without rescreening the study participant.

6. Study Intervention

[figure not shown]
Study intervention is defined as any investigational intervention(s), marketed product(s), placebo, or medical device(s) intended to be administered to a study participant according to the study protocol.

6.1. Study Intervention(s) Administered

LY3209590 will be provided in a 20 mg vial of lyophilized powder. Upon reconstitution per the pharmacy instructions provided by the sponsor, LY3209590 will be administered once weekly as SC injections. Each patient will receive 1 injection each week, as described in the “Treatment Regimens” table below. SC injections of LY3209590 will be administered rotating between left and right abdominal regions, and upper and lower quadrants. Refer to Study Period 2 in Section 4.1.1 for details on how IP will be administered.

Patients will receive treatment with LY3209590 by an algorithm described in Section 10.8.

The LY3209590 Algorithm 1 is a paper-based algorithm that uses similar principals to the established Riddle algorithm.

Insulin degludec will use the established Riddle algorithm and is a paper-based algorithm.

Approximately one-half of the subjects will be randomized in each of the 2 remaining treatment arms.

Insulin degludec will be provided as 100 units/mL in a prefilled pen. It will be administered once daily at approximately the same time of day, rotating between left and right abdominal regions, and upper and lower quadrants.

See Section 6.7.1 for transitioning to treatment after study completion.

Treatment Regimens

Regimen	Dose Randomization through Week 26
LY Dose Algorithm 1 (paper)	LY injection
Insulin degludec	insulin degludec injection (open-label)

Abbreviations: LY = LY3209590.

The investigator or his/her designee is responsible for the following:

- explaining the correct use and reconstitution of the investigational agent(s) to the patient
- verifying that instructions are followed properly
- maintaining accurate records of IP dispensing and collection
- at the end of the study returning all unused medication to Lilly, or its designee, unless the sponsor and sites have agreed all unused medication is to be destroyed by the site, as allowed by local law

Clinical study materials will be labeled according to the country's regulatory requirements.

6.1.1. Selection and Timing of Doses

For patients randomly assigned to LY3209590, a loading dose will be determined using Table 1 in Algorithm 1 (see Section 10.8). The weekly dose adjustment thereafter will be based on guidance provided in Section 10.8. The doses will be administered at approximately the same time and day each week. The actual date, time and dose of each dose administrations (LY3209590 and insulin degludec) will be recorded in the participant's diary (and participant's medical record when administered at the site).

If a patient misses a scheduled dose of LY3209590, it should be administered as soon as possible, but no later than 3 days after the scheduled administration. If more than 3 days have elapsed since the scheduled administration, the dose should be skipped and the next injection will occur at the next scheduled day and time.

Insulin degludec should be administered at the same time each day adjusted per the modified Riddle algorithm (Section 10.8).

Patients who miss a dose of insulin degludec should inject their daily dose during waking hours upon discovering the missed dose. Instruct patients to ensure that at least 8 hours have elapsed between consecutive insulin degludec injections (Tresiba® USPI).

For details on the titration algorithms to be used, refer to Section 10.8.

6.1.2. Special Treatment Considerations

6.1.2.1. Standards of Medical Care

Investigators and other study team members are expected to treat patients according to the nationally established standards of care for diabetes management in respective participating countries, except where that treatment would be in conflict with the protocol-provided treatment requirements. If there are no local standards of care for diabetes, the investigators should follow current published standards of care from the American Diabetes Association (2016) and the European Association for Study of Diabetes (Inzucchi et al. 2015) during their patients' participation in this study. Standards of prevention of persistent hyperglycemia and ketone monitoring must be followed during the course of the study to prevent DKA.

Patients will continue their short acting insulin treatment throughout the duration of the study. Investigators are responsible to adapt mealtime and correction bolus dosing according to

standards of medical care. When titrating basal insulin a reduction of the mealtime insulin is necessary in most cases and should be considered by investigators to prevent hypoglycemia.

This section provides guidance on management of episodes of hypoglycemic events and events of severe, persistent hyperglycemia. For effective implementation of measures described here, it is important that patients, and their caregivers, if applicable, be well-educated about the signs and symptoms of hyperglycemia (e.g., severe thirst, dry mouth, frequent micturition, or dry skin) and hypoglycemia (e.g., intense hunger, sweating, tremor, restlessness, irritability, depression, headaches, disturbed sleep, or transient neurological disorders). Patients should be instructed to contact the investigative site in the event of severe, persistent hyperglycemia or severe hypoglycemia between study visits.

6.1.2.2. Management of Increased Hypoglycemia Risk

To date, effects of LY3209590 on hypoglycemia in patients with T2DM are not different as compared to other basal insulins. An objective of the study is to assess the risk of hypoglycemia in T1DM patients receiving LY3209590 as compared to insulin degludec.

In this study, increased risk of hypoglycemia is defined as having a single episode of severe hypoglycemia or having more than 1 episode of documented hypoglycemia with $BG < 54 \text{ mg/dL}$ within a 1-week period at any time during the treatment period. Documented hypoglycemia is defined as any time a participant reports a SMBG $\leq 70 \text{ mg/dL}$ ($< 3.9 \text{ mmol/L}$) or any investigator confirmed case of severe hypoglycemia.

In cases where a patient experiences hypoglycemia as described above, to confirm the increased risk, the study sites must ensure that the patient has been fully compliant with the assigned therapeutic regimen and also that there is no evidence of other possible causes of hypoglycemia (e.g., omission of meal, inadequate meal or correction bolus, unexpected increase in exercise).

Patients fulfilling the definition of increased risk of hypoglycemia should first correct their bolus dosing, then decrease their dose of IP per the respective dosing algorithm, followed by discontinuation of IP, if needed.

6.1.2.3. Management of Patients with Severe, Persistent Hyperglycemia during the Treatment Period

Transient hyperglycemia may be observed during the first 1 to 2 weeks of treatment with LY3209590 and additional correction doses of rapid acting insulin may be used to manage hyperglycemia during this transition period.

An additional therapeutic intervention should be considered in patients who develop severe, persistent hyperglycemia after randomization based on the following criteria (FDA 2008):

- a) average fasting glucose (FG) $> 270 \text{ mg/dL}$ ($> 15.0 \text{ mmol/L}$) over any 2-week period or longer during the first 6 weeks postrandomization; or
- b) average FG $> 240 \text{ mg/dL}$ ($> 13.3 \text{ mmol/L}$) over any 2-week period or longer from Week 6 to Week 12 postrandomization; or
- c) average FG $> 200 \text{ mg/dL}$ ($> 11.1 \text{ mmol/L}$) over any 2-week period or longer after Week 12.

Investigators should first confirm that the patient does not have an acute condition causing severe hyperglycemia, and after the first 12 weeks of the study, that the patient is fully compliant with the assigned therapeutic regimen. The investigator will decide, in consultation with the patient, on an appropriate intensification of insulin therapy after considering relevant clinical criteria. Patients who receive a new intervention for hyperglycemia management should also continue administering IP for the remaining period in the trial.

6.1.3. Medical Devices

The sponsor will provide syringes for subcutaneous injection.

6.2. Preparation/Handling/Storage/Accountability

The investigator or designee must confirm appropriate temperature conditions have been maintained during transit for all study intervention received and any discrepancies are reported and resolved before use of the study intervention.

Only participants enrolled in the study may receive study intervention and only authorized site staff may supply or administer study intervention. All study intervention must be stored in a secure, environmentally controlled, and monitored (manual or automated) area in accordance with the labeled storage conditions with access limited to the investigator and authorized site staff.

The investigator, institution, or the head of the medical institution (where applicable) is responsible for study intervention accountability, reconciliation, and record maintenance (i.e., receipt, reconciliation, and final disposition records).

Further guidance and information for the final disposition of unused study interventions will be provided by the sponsor.

The study site must store all study intervention in a locked and secure environment.

Investigators should consult the study drug information provided in the Pharmacy Instructions or label for the specific administration information (including warnings).

6.3. Measures to Minimize Bias: Randomization and Blinding

This is an open-label study; thus, it will be unblinded. However, the specific intervention to be taken by a participant will be assigned using an Interactive Web Response System (IWRS). The site will contact the IWRS prior to the start of study intervention administration for each participant. The site will record the intervention assignment in the appropriate data capture tool. Potential bias will be reduced by the following steps: central randomization, stratification, blinded adjudication for CV endpoints.

Patients who meet all criteria for enrollment will be randomized to treatment at Visit 3. Assignment to treatment groups will be determined by a computer-generated random sequence using the IWRS. The IWRS will be used to assign IP to each patient. Site personnel will confirm that they have located the correct IP by entering a confirmation number found on the IP label into the IWRS.

To achieve between-group comparability for site factor, the randomization will be stratified by baseline HbA1c (<8.5%, \geq 8.5%), and country. The randomization scheme will be performed using IWRS, which will ensure balance between treatment groups.

6.4. Study Intervention Compliance

The assessment of treatment compliance with IP (LY3209590 or insulin degludec) will be determined by the following:

- Information about the once weekly IP injections administered at home by the patient will be entered into the patient diary by the patient and reviewed by the site personnel at each study visit; this information will be collected in the electronic study diary;
- IP accountability will be checked according to the Schedule of Activities (Section 1.3). Study participants will be instructed to return all dispensed vials, any *unused* pens, and/or all empty cartons at the next visit to the study site for the purpose of performing drug accountability.

Other aspects of compliance will also be assessed at each visit, including the patient's adherence to the visit schedule, compliance with the concomitant short acting insulin requirements and other medication guidances (Section 6.5), completion of study diaries, results of SMBG through CGM, and any other parameters the investigator considers necessary. Patients considered to be poorly compliant with their medications and/or study procedures (e.g., missed visits or specific diagnostic tests) will receive additional training and instructions, as required.

When participants are dosed at the site, they will receive IP directly from the investigator or designee, under medical supervision. The date and time of each dose administered in the clinic will be recorded in the source documents and recorded in the diary.

When participants administer study treatment at home, compliance with study treatment will be assessed at each visit. Compliance will be assessed by direct questioning, reviewing eCOA documentation, counting returned pens, etc. during the site visits.

A record of the number of the pens and study medications dispensed to and taken by each participant must be maintained and reconciled with study intervention and compliance records. Intervention start and stop dates, including dates for intervention delays and/or dose reductions will also be recorded in the electronic case report form (eCRF).

6.5. Concomitant Therapy

Any medication or vaccine (including OTC or prescription medicines, vitamins, and/or herbal supplements) or other specific categories of interest) that the participant is receiving at the time of enrollment or receives during the study must be recorded in the eCRF along with:

- Reason for use
- Dates of administration including start and end dates, and
- Dosage information including dose and frequency for concomitant therapy of special interest.

Lilly Medical should be contacted if there are any questions regarding concomitant or prior therapy.

Participants will be permitted to use concomitant medications that they require during the study, except prohibited medications described in Section 5.2 and Sections 6.5.1 and 6.5.2 below. In addition, certain permitted medications (e.g., treatments for blood pressure or dyslipidemia) described in Sections 6.5.3 and 6.5.4 should be continued, but not changed, during the study.

Participants will continue to use concomitant short-acting insulin throughout the treatment period. Discontinuation or changes to regimen are not permitted, except in situations where dose adjustment is required for medical reasons or when allowed per study protocol.

Investigative site staff will inform patients that they must consult with the investigator or a designated site staff member upon being prescribed any new medications during the study, except when initiated for treatment of medical emergencies.

Non-study medications taken by patients who are screened but not randomized will not be reported to Lilly unless an SAE or AE occurs that the investigator believes may have been caused by a study procedure.

6.5.1. Medications that Promote Weight Loss

Prescription or OTC medications that promote weight loss are exclusionary if used within the 3 months prior to screening, or any time after screening (see Section 6.5). If started after screening, these medications should be stopped immediately. In addition, patients should not receive an intensive diet/exercise program with the intent of reducing body weight at any time during the study, other than the lifestyle and dietary measures for diabetes treatment (see Section 5.3).

6.5.2. Systemic Glucocorticoids

Chronic systemic glucocorticoid therapy (excluding topical, intraocular, intranasal, or inhaled preparations) is exclusionary if used >14 consecutive days during the 1-month period before screening or between screening and randomization at Visit 3.

Patients treated with these medications after randomization will be excluded from the efficacy evaluable population for analyses if they receive:

- >14 days consecutive days of therapy, or
- More than 1 course of therapy during the study.

6.5.3. Antihypertensive Medications

If used, anti-hypertensive therapy should be kept stable throughout the trial to allow assessments of the effect of randomized therapies on blood pressure.

6.5.4. Dyslipidemia Medication

If used, dyslipidemia therapy should be kept stable throughout the trial to allow assessments of the effect of randomized therapies on lipid endpoints.

6.6. Dose Modification

Dosing of basal insulin will be individualized based on FG. See Section 10.8 for details of dose modification.

6.7. Intervention after the End of the Study

After the end of the treatment period patients should continue to monitor their FG levels. The treating physician should then make the decision based on local clinical practice, if and what additional antihyperglycemic treatment needs to be administered.

Investigational product will not be made available to patients after conclusion of the study. After IP is discontinued, an appropriate diabetes treatment regimen will be initiated by the investigator.

6.7.1. Treatment after Study Completion

The last study treatment administration for patients treated with LY3209590 will be at Week 25 and for patients treated with insulin degludec the evening before the last study visit at Week 26. The washout of LY3209590 may take up to 10 weeks to complete. Any appropriate basal insulin treatment must therefore be instituted slowly and under regular supervision of BG profiles after discontinuation of LY3209590. Since CCI [REDACTED]

[REDACTED] Therefore, a slow up-titration of another basal insulin is necessary to prevent hypoglycemia due to overlapping insulin action. For example, no insulin would be required until the study participant's FG increases to >100 mg/dL, and then daily basal insulin would be initiated and adjusted based on FG.

Study participants assigned to the insulin degludec treatment group will switch to the basal insulin used before entering the study. If insulin degludec was the pre-study basal insulin, they can continue with the same dose used until Visit 20 of the study. If they switch to another basal insulin (e.g., insulin glargine), study participants should inject a daily dose, which is 20% lower than the last dose of insulin degludec used before Visit 20 and titrate under supervision of the investigator using the country-specific label for their pre-study basal insulin.

7. Discontinuation of Study Intervention and Participant Discontinuation/Withdrawal

7.1. Discontinuation of Study Intervention

Study drug may be permanently discontinued or temporarily withheld during the study.

Participants who permanently discontinue study drug early will undergo ET procedures, which include

- an ET visit or,
- post-treatment follow-up visits (ED 1, ED 2).

The investigator will complete any AE reporting and necessary follow-up.

7.1.1. Permanent Discontinuation from Study Treatment

Possible reasons leading to permanent discontinuation of investigational product include, but are not limited to:

- **Participant decision**
 - the patient or the patient's designee, for example, parents or legal guardian requests to discontinue IP.
- **Hepatic event or liver test abnormality:** Participants who are discontinued from IP due to a hepatic event or liver test abnormality should have additional hepatic safety data collected via eCRF

Discontinuation of the IP for abnormal liver tests **should be** considered by the investigator when a participant meets one of the following conditions after consultation with Lilly Medical

- ALT or AST >8x ULN
- ALT or AST >5X ULN for more than 2 weeks
- ALT or AST >3X ULN and TBL >2X ULN or international normalized ratio (INR) >1.5
- ALT or AST >3X ULN with the appearance of fatigue, nausea, vomiting, right upper-quadrant pain or tenderness, fever, rash, and/or eosinophilia (>5%)
- ALP >3X ULN
- ALP >2.5X ULN and TBL >2X ULN
- ALP >2.5X ULN with the appearance of fatigue, nausea, vomiting, right quadrant pain or tenderness, fever, rash, and/or eosinophilia (>5%)

In addition, participants will be discontinued from the IP in the following circumstances:

- If a patient is inadvertently enrolled and it is determined that continued treatment with IP would not be medically appropriate (see Section 7.2.1)

- if a patient is diagnosed with an active or untreated malignancy (other than basal or squamous cell skin cancer, in situ carcinomas of the cervix, or in situ prostate cancer) after randomization
- if the investigator or sponsor decides that the patient should be withdrawn from IP; if the investigator decides to permanently discontinue IP because of an SAE or a clinically significant laboratory value, Lilly or its designee should be alerted immediately
- if the investigator, after consultation with Lilly Medical, determines that a systemic hypersensitivity reaction has occurred related to study drug administration, the participant should be permanently discontinued from IP.

See the Schedule of Activities (Section 1.3) for data to be collected at the time of intervention discontinuation and follow-up and for any further evaluations that need to be completed.

Patients who stop the IP permanently may receive another glucose-lowering intervention, if appropriate, and will continue participating in the trial according to the protocol to collect all planned efficacy and safety measurements.

7.1.2. Temporary Discontinuation

In certain situations after randomization, the investigator may need to temporarily discontinue (interrupt) IP (e.g., due to an AE or a clinically significant laboratory value). The maximum time allowed for a temporary interruption of IP is 14 days. If IP interruption is due to an AE, the event is to be documented and followed according to the procedures in Section 8.3 of this protocol. Investigators should inform the sponsor that IP has been temporarily interrupted. Every effort should be made by the investigator to maintain patients on IP and to restart IP after any temporary interruption, as soon as it is safe to do so. The data related to temporary interruption of IP and use of non-study insulin will be documented in source documents and entered in the eCRF.

7.2. Participant Discontinuation/Withdrawal from the Study

A participant will be discontinued (withdrawn) from the study in the following circumstances:

- if he or she is diagnosed with any type of diabetes mellitus other than T1DM
- at any time at his/her own request
- at the discretion of the investigator for safety, behavioral, compliance, or administrative reasons
- if the participant becomes pregnant during the study
- if enrollment in any other clinical study involving an investigational product or enrollment in any other type of medical research judged not to be scientifically or medically compatible with this study
- participation in the study needs to be stopped for medical, safety, regulatory, or other reasons consistent with applicable laws, regulations, and good clinical practice (GCP)
- investigator decision
 - the investigator decides that the participant should be discontinued from the study

- if the participant, for any reason, requires treatment with another therapeutic agent that has been demonstrated to be effective for treatment of the study indication, discontinuation from the study occurs prior to introduction of the new agent
- participant decision:
 - the patient or the patient's designee, for example, parents or legal guardian requests to be withdrawn from the study

Discontinuation is expected to be uncommon.

At the time of discontinuing from the study, if possible, an early discontinuation visit should be conducted, as shown in the Schedule of Activities (Section 1.3). See Schedule of Activities for data to be collected at the time of study discontinuation and follow-up and for any further evaluations that need to be completed. The participant will be permanently discontinued both from the study intervention and from the study at that time.

If the participant withdraws consent for disclosure of future information, the sponsor may retain and continue to use any data collected before such a withdrawal of consent. If a participant withdraws from the study, he/she may request destruction of any samples taken and not tested, and the investigator must document this in the site study records.

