All randomized participants should have a comprehensive efficacy and safety evaluation approximately 1 week after the last dose of LY3209590 and 1 day after the last dose of insulin degludec, and a safety follow-up visit approximately 6 weeks after the last dose of LY3209590 and 5 weeks after the last dose of insulin degludec. During the safety follow-up study period, participants will continue CGM and will be switched back to their previously used basal insulin therapy if appropriate (see Section 6.7.1). Participants will also be required to return any remaining used or unused IP at Visit 20 and the eDiary at Visit 801 to the investigative site.

Participants who *complete the treatment period* will have a comprehensive End-of-Treatment efficacy and safety assessment (Week 26; Visit 20) approximately 1 week after the last dose of

LY3209590 and 1 day after last dose of insulin degludec and a safety follow-up assessment (Visit 801) approximately 6 weeks after the last dose of LY3209590 and 5 weeks after the last dose of insulin degludec.

Participants who *discontinue IP prior to completion* of the treatment period for any reason should follow the visit schedule off study drug and also have a comprehensive End-of-Treatment efficacy and safety assessment (ED 1) approximately 1 week after the last dose of LY3209590 and 1 day after the last dose of insulin degludec or as soon as reasonably possible thereafter, and should have a safety follow-up assessment (ED 2) approximately 6 weeks after the last dose of LY3209590 and 5 weeks after the last dose of insulin degludec. Study activities at Visits ED 1 and ED 2 are identical to Week 26 (Visit 20) and Visit 801, respectively. This close follow-up is necessary since LY3209590 has a **CCI** and the switch to an alternative, commercially available insulin must be closely monitored to prevent hypoglycemia due to an accumulation of insulin action.

Participants who discontinue IP prior to the completion of the treatment period will be encouraged to remain in the study and to complete any scheduled study procedures that occur until Visit 20. Participants remaining in the study will receive an appropriate glucose-lowering regimen.

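### Protocol 7.2, read literally, withdraws from the study participants whom 4.1.1 and 7.1.1 keep in it on another glucose-lowering treatment

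*Protocol*

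**What the plan says.** Protocol 7.2 lists circumstances in which a participant will be withdrawn from the study. One bullet states that, for a participant who for whatever reason needs "another therapeutic agent that has been demonstrated to be effective for treatment of the study indication, discontinuation from the study occurs prior to introduction" of that agent. The section then adds: "The participant will be permanently discontinued both from the study intervention and from the study at that time".

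Protocol 7.1.1 says of patients whose IP is stopped for good that they "may receive another glucose-lowering intervention, if appropriate, and will continue participating in the trial according to the protocol to collect all planned efficacy" data, together with safety data.

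Protocol 4.1.1 (Study Period 3) says that those who stop IP before the end "of the treatment period for any reason should follow the visit schedule off study drug", that they "will be encouraged to remain in the study and to complete any scheduled study procedures that occur until Visit 20", and: "Participants remaining in the study will receive an appropriate glucose-lowering regimen". Footnote c of the Schedule of Activities assigns visits ED1 and ED2 to people who are off drug but still in the study.

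Three other places deal with added or non-study treatment, and none makes it a reason to leave:
- Protocol 4.1.1 (General considerations): after unscheduled insulin intensification, the participant continues IP and completes all visits.
- Protocol 6.1.2.3: after a new intervention for hyperglycemia, the participant continues IP.
- Protocol 7.1.2: during a temporary interruption of up to 14 days, non-study insulin is recorded and IP is restarted when safe.

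SAP 5.7 builds the primary estimand on data up to the end of study treatment. Its supportive estimand uses every available Week 26 value, on or off treatment, and imputes values missing through early study discontinuation by return to baseline.

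**The concern.** The two sets of instructions give opposite answers for the same person. IP is the basal insulin, and participants have type 1 diabetes with fasting C-peptide of at most 0.30 nmol/L (Protocol 5.1). Someone who stops IP will ordinarily need another basal insulin, and Appendix 10 says so for its setting. Basal insulin is an effective agent for the indication. Taken at its word, the 7.2 bullet therefore leaves the retention rule in 7.1.1 with almost nobody to apply to. Nothing in the protocol says which instruction prevails.

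What is at stake is off-treatment data. The supportive estimand needs Week 26 HbA1c from people who have stopped IP. A site that follows 7.2 turns an obtainable measurement into an imputed one, and different sites may act differently. Follow-up during the switch away from a long-acting insulin also becomes unclear.

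**Working it through.** **1. The rules side by side**

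| Situation | Other protocol text | 7.2 bullet, read literally |
|---|---|---|
| IP stopped permanently, another basal insulin needed | 4.1.1, 7.1.1: stays in the study, scheduled visits to Visit 20, ED1 and ED2 | Withdrawn before the replacement starts |
| Severe persistent hyperglycemia on IP, treatment added | 4.1.1, 6.1.2.3: continues IP and visits | Withdrawn if the addition counts as another effective agent |
| IP interrupted for up to 14 days, non-study insulin used | 7.1.2: recorded, IP restarted when safe | Withdrawn before the non-study insulin starts |

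Row 1 is a direct contradiction, chiefly with the visit-schedule instruction in 4.1.1 and the continued participation in 7.1.1. The other two 4.1.1 statements are softer: one encourages, and the other applies to people who do remain. Rows 2 and 3 show that the literal bullet also fits badly with the rest of the protocol.

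**2. Which analyses are reached**

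- Primary estimand: it uses data only up to treatment discontinuation, so retention after IP stops does not enter it. It would be touched only in the row 2 situation, if a site withdrew a rescued participant who should have stayed on IP.
- Supportive estimand: reached, through Week 26 values that become missing.
- Safety follow-up: ambiguous. Protocol 4.1.1 asks for "a safety follow-up visit approximately 6 weeks after the last dose of LY3209590 and 5 weeks after the last dose of insulin degludec" for all randomized participants, and 7.2 itself says "See Schedule of Activities for data to be collected at the time of study discontinuation and follow-up and for any further evaluations".

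**3. How many values could depend on the rule**

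Base (Protocol 9.2): 190 / 0.8 = 237.5, rounded up to 238, or 119 per arm. The 20% there is dropout from the study. It is not the share who stop IP and would stay, which the documents do not give. Assumed shares:

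| Share who stop IP and would stay | Of 238 | Per arm of 119 |
|---|---|---|
| 2% | 4.8 | 2.4 |
| 5% | 11.9 | 6.0 |
| 10% | 23.8 | 11.9 |

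This base is approximate. SAP 5.7 words the supportive analysis for all randomized and dosed patients with a baseline value, which may not be the same set as the 238.

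**4. Effect on the supportive difference**

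Let s be the fraction per arm whose Week 26 value is lost, and c their mean off-treatment HbA1c change. Return to baseline replaces c by a mean change of 0. Ignoring covariate adjustment and imputation noise, the difference (LY3209590, L, minus degludec, D) shifts by

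shift = −(sL·cL − sD·cD).

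- Equal s and equal c: 0.
- s = 5% in both arms, cL − cD = ±0.3: −(0.05 × ±0.3) = ∓0.015.
- sL = 10%, sD = 5%, c = −0.5 in both: −(−0.050 + 0.025) = +0.025. With the stop rates reversed: −0.025.

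For scale, 0.015 / 0.4 = 3.75% and 0.025 / 0.4 = 6.25% of the non-inferiority margin, which the SAP does not apply to this estimand. Every s and c here is an assumption.

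**The case against.** The best defence is that 7.2 was never meant to cover insulin. All participants take rapid-acting insulin throughout, intensification and non-study insulin are allowed in the study, and Appendix 10 has alternative treatment supplied through safety follow-up. Exclusion 32 names diabetes drugs other than rapid-acting and basal analog insulin, and Protocol 6.5 carries the prohibitions of 5.2 into the study. The intervention allowed by 7.1.1 is qualified by appropriateness and by the protocol. Read together, 7.1.1 can mean insulin and 7.2 can mean prohibited non-insulin agents. On that reading the number of participants affected is near 0.

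Much of this stands. A reader might infer that the protocol nowhere allows non-study insulin without withdrawal; 7.1.2 shows that it does. A reader might also infer that the conflict with 7.1.1 survives the narrower reading, since 7.1.1 does not limit itself to insulin; given its qualifiers, the documents do not establish that. What remains is that the narrower meaning has to be pieced together from other sections. The bullet applies whatever the reason, makes no exception for insulin, and is followed by a sentence taking the participant off both IP and study.

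**Conclusion.** The point holds as a contradiction in current text between the literal 7.2 bullet and the retention rules in 4.1.1 and 7.1.1. It is minor. Confidence is high for the wording conflict and low for any practical effect, which depends on how sites read the bullet.

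The size cannot be determined from the documents and is likely small: near 0 participants on the narrower reading, and about 5 to 24 Week 26 values on the literal reading if 2% to 10% stop IP and would stay. The direction is also undetermined.

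Two stronger conclusions are not supported. One is that the non-inferiority decision is at risk: the primary estimand does not use data after IP stops, and only misapplication to participants rescued on IP could reach it. The other is that safety follow-up is lost: 4.1.1 requests it for everyone randomized and 7.2 points to the Schedule of Activities, so it is unclear rather than absent.

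**What to change.** Delete the bullet, or reword it to say that starting another glucose-lowering agent, including replacement or additional insulin, is not a reason for study withdrawal. The replacement wording should separate two cases:
- Participants rescued for hyperglycemia continue IP, as 4.1.1 and 6.1.2.3 already require.
- Participants who stop IP permanently stay for scheduled visits through Visit 20 and for ED1 and ED2, as in 4.1.1 and 7.1.1.

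The separation matters: a rewording that merely turned the bullet into a reason to stop IP would contradict the first case. The other withdrawal reasons in 7.2 can stand. The cost is the wording of one bullet. No visit or assessment is added, because the off-drug schedule, ED1 and ED2 already exist.
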